## 5.5. Pharmacokinetic Concentration Analysis Set

The PK Concentration Analysis Set comprises participants who have consented to participate in the PK substudy, in adolescent cohort and in the main study, have received at least 1 dose of brensocatib, and have at least 1 post-dose plasma concentration of brensocatib, excluding participants from Ukraine and participants from site USA065. Participants will be classified according to actual treatment received regardless of the treatment group to which they were randomized.

## 5.6. CT Scan Analysis Set

The CT Scan Analysis Set comprises participants who have both baseline and post-baseline CT measurement data, excluding participants from Ukraine and participants from site USA065. The CT Scan Analysis Set will be analyzed using the actual treatment received.

Participants with non-missing consent date to participate in the CT substudy and with non-missing baseline and post-baseline CT data available will be included in this analysis set for all CT summaries and statistical analyses.

CONFIDENTIAL Page 24 of 139

#### 6. GENERAL STATISTICAL CONSIDERATIONS

The statistical software package SAS® Version 9.4 (SAS Institute, Cary, NC, USA) will be used to perform all analyses and to summarize data.

#### 6.1. General

All summaries will be provided by treatment group, if not stated otherwise (see Section 6.4.2 below). Some presentations will describe specific populations, and this will be evident in each output as necessary.

Descriptive statistics for continuous variables will be calculated at scheduled visits (nominal time points for PK concentration) and will include the number of participants in the treatment group/dose level of the respective Analysis Set (N in column header of the table), the number of non-missing observations (n), arithmetic mean, standard deviation (SD), CV%, median, minimum, and maximum. For NSP concentrations and percent change from baseline in blood and sputum, mean, SD, CV%, median, minimum, maximum will be determined. For brensocatib plasma concentrations and PD results, the geometric mean (GM) with 95% CI and geometric coefficient of variation -percentage (gCV)%, and the number of observations below limit of quantification (BLQ) will also be reported. The GM will be derived by calculating the arithmetic mean of the log-transformed observations and then back-transforming the mean by exponentiation. The gCV% will be calculated as: 100\*sqrt (exp [variance of the log-transformed values] - 1). GM -and gCV% will only be calculated for quantifiable values above 0 (if at least 1 value are less than 0, e.g., for PD parameters, no GM and gCV% will be displayed but left empty). Listings will present the data in its original format.

Categorical variables will be summarized by counts and by percentage of participants in the corresponding categories. The number of participants in the treatment group/dose level of the respective Analysis Set (N in column header of the table) and the number and percentage of non-missing observations in each category will be provided. A category including missing assessments may be added if appropriate. Footnotes will specify the denominator used for the percentages.

In case of mis-randomization to incorrect strata, participants will be analyzed according to the strata into which they were randomized.

Data from unscheduled visits will not be used in summaries, except for the derivation of baseline (see Section 6.4.3).

If not specified otherwise, reported p-values and confidence intervals will be 2-sided. P-values greater than or equal to 0.001 will be presented to three decimal places. P-values less than 0.001 will be presented as "<0.001". Confidence intervals will be presented to one more decimal place than the estimate.

All efficacy and safety data that have already been collected from the Ukraine or from site USA065 will be listed only and not included in the formal efficacy and safety analyses of ASPEN data. Listings will be produced for AE, demography and baseline characteristics, and IP exposure. The Ukraine and site USA065 listings will remain separate from the rest of the

CONFIDENTIAL Page 25 of 139

study data for ease of review. Note: The originally planned sample size of 1,620 participants will not include participants from Ukraine or participants from site USA065.

## **6.2.** Considerations for Constructing Estimands

Analysis of the On-Study Estimands will be conducted in the ITT Analysis Set (see Section 5.2) in which all observed data will be included regardless of whether the participants remain on randomized IP. This Estimand will be considered the Primary Estimand and utilizes the Treatment Policy strategy for ICEs (see Section 2). Analyses of the On-IP and On-Treatment Estimands will be conducted using the ITT Analysis Set for efficacy endpoints.

For all On-Study Estimands for the primary and secondary endpoints in the multiple testing procedure, tipping point sensitivity analysis will only be conducted if the main results are statistically significant.

A blinded data review meeting (BDRM) will be conducted to review the definition of analysis sets, the assignment of participants into the analysis sets, as well participants meeting criteria for ICEs of the study Estimands (see Section 2). A data review report (DRR) will be prepared and signed prior to database lock and unblinding to document participant's assignment into analysis sets and agreed actions for participants meeting any ICE criteria prior to database lock and unblinding. Any incorrect treatment assignments determined subsequent to database lock and unblinding will be included in the DRR minutes as an addendum.

Analysis details are presented in Section 9.

#### **6.2.1.** Identification of ICEs

The following subsections will describe the two ICEs defined for this study.

If both ICEs occur at the same date, e.g., early discontinuation from randomized IP and modification from standard of care at the same date, the early discontinuation from randomized IP will be prioritized. Within standard of care the discontinuation from standard of care will be prioritized over addition of new chronic antibiotics.

#### 6.2.1.1. Early Discontinuations from Randomized IP

Early discontinuation from randomized IP will be identified through the eCRF "End of treatment". A participant will be considered as early discontinued from randomized IP if the question "Did the subject complete the planned treatment per protocol?" was answered with "No".

The date entered for "Last dose date" will be used as date of ICE onset.

# 6.2.1.2. Modifications to Standard of Care: Addition/Discontinuation Chronic Antibiotics

The addition of a new chronic antibiotic treatment or discontinuation from standard of care (i.e., baseline chronic antibiotics) is defined as any change of the chronic antibiotics that was stable at baseline. For additional evaluation, this ICE may be broken down into the subtypes:

CONFIDENTIAL Page 26 of 139

"Initiating new Chronic Antibiotics", "Adding a new Chronic Antibiotic to the Existing Chronic Antibiotic Regimen", and "Changing Chronic Antibiotics" given their derivation in the sub-sections below.

Participants discontinuing from standard of care with no replacement, e.g., no new use of antibiotics, will be counted separately. Any changes in dose or frequency of the same chronic antibiotics within 7 days will NOT be counted as discontinuation from standard of care as it is considered as continuation of the standard of care therapy. Example, if chronic antibiotic A which was present at baseline stopped and restarted within 7 days with the same or a modified dose or frequency, the chronic antibiotic A will not be considered as discontinuation from standard of care.

Special care will be taken for partially reported dates of standard of care therapy. Please refer to Section 6.9.2 for further details.

Any standard of care stopped at the same date as IP administration stop date will not be considered as an ICE.

Due to its nature this data is complex and requires additional methods. Please refer to Appendix M for further details.

#### **6.2.1.2.1.** Initiating new Chronic Antibiotic Treatment

Initiation of chronic antibiotics will be identified through entries in eCRF "*Prior and concomitant medications*". World Health Organization (WHO) Drug dictionary codes provided in Appendix K will be used to identify start of new chronic antibiotics. The start date of the new chronic antibiotic must be on or after the date of randomization, and at least 7 days from the end of the previous therapy, if applicable. The date entered for "*Start date*" will be used as date of ICE onset.

Note: it is expected that first IP administration is administered at the date of randomization (refer to Section 6.4.2). In circumstances where the date of first IP is not equal to the date of randomization, the date of first IP administration will be used as reference date. Hence, the start date of the new chronic antibiotic must be on or after the date of first IP administration. This rule applies to the below two sub-sections, too.

### 6.2.1.2.2. Adding a New Chronic Antibiotic to the Existing Chronic Antibiotic Regimen

Adding a new chronic antibiotic to an existing chronic antibiotic regimen will be identified through entries in eCRF "*Prior and concomitant medications*". WHO Drug dictionary codes provided in Appendix K will be used to identify addition of new chronic antibiotics. This ICE subtype applies only in cases where the participant has already (at least) one record for taking chronic antibiotics at time of randomization. The start date of the new chronic antibiotic must be on or after the date of randomization.

The date entered for "Start date" will be used as date of ICE onset.

CONFIDENTIAL Page 27 of 139

## 6.2.1.2.3. Changing Chronic Antibiotics

Changing existing chronic antibiotics will be identified through entries in eCRF "*Prior and concomitant medications*". WHO Drug dictionary will be used to identify existing and new chronic antibiotics. This ICE subtype applies only in cases where:

- the participant has already (at least) one record for taking chronic antibiotics at time of randomization,
- the start date of the new antibiotic is on or after the date of randomization,
- the existing chronic antibiotic has a stop date entered and the same has not been restarted within 7 days after the stop. Change in dose or frequency of the same chronic antibiotics will be considered as restart,
- the start date of the new antibiotic is within 7 days commencing the stop date of the existing chronic antibiotic.

The date entered for "End date" of the existing chronic antibiotic will be used as date of ICE onset.

#### 6.2.2. Time to (first) ICE

Time to first ICE in days will be calculated as

Time to (first) ICE (days) = start date of first ICE - date of reference + 1.

Participants who do not have an ICE during the 52-Week treatment period will be censored at time of EOT.

The date of reference will be the date of first IP administration, if not stated otherwise. If a participant was randomized but not treated with IP, the participant will be censored at study day 1 (day of randomization).

# **6.3.** Multiple Comparisons and Multiplicity Adjustment

The study has 3 treatment groups (brensocatib 25 mg, brensocatib 10 mg, and placebo), 1 primary endpoint, and 5 secondary efficacy endpoints. The annualized rate of PEs is the primary efficacy endpoint. The time to first pulmonary exacerbation, the responder status for being exacerbation free over the 52 weeks, the change in post-bronchodilator FEV1 at Week 52, the annualized rate of severe PEs, and the change in QoL-B respiratory symptoms domain score at Week 52are the secondary efficacy endpoints. The overall type I error rate control will focus on the comparisons of the two brensocatib doses relative to placebo for the primary endpoint and all these five secondary endpoints.

In this study, the enhanced mixture-based gatekeeping procedure (Kordzakhia et al, 2018) is used as the multiplicity adjustment method to control the overall type I error rate at a full alpha ( $\alpha = 0.05$ ) with a two-sided test for the multiple tests of the 12 null hypotheses ( $H_1, H_2, ..., H_{12}$ ) listed in Table 3 below. The enhanced mixture-based method is based on the closed testing procedure and thus protects the overall type I error rate in a strong sense. Adjusted p-values will be reported.

CONFIDENTIAL Page 28 of 139

To demonstrate substantial evidence of effectiveness, the adjusted p-values for the comparisons of brensocatib 25 mg versus placebo and brensocatib 10 mg versus placebo for the primary endpoint, the annualized rate of PEs, will also be compared against the two-sided  $\alpha = 0.01$ .

#### 6.3.1. Families and Hypotheses

With the 6 efficacy variables, 6 families are constructed, respectively, as Family 1 through Family 6, which are indexed from 1 to 6 according to the order of clinical importance, as shown in Table 3. This table lists the null and alternative hypotheses by family for each pairwise comparison in the Multiplicity Adjustment procedure. Each family has two null hypotheses (one for each of the brensocatib doses in comparison to placebo).

Table 3: Families (Endpoint/Dose) and Hypotheses in Multiplicity Adjustment

Null and Alternative Hypotheses by Family

Null and Alternative Hypotheses by Family		
Brensocatib 25 mg vs Placebo	Brensocatib 10 mg vs Placebo	
Family 1: Annualized Rate of PEs (Rate Ratio)		
$H_1: \frac{\lambda_H}{\lambda_P} = 1 \text{ vs } H_{11}: \frac{\lambda_H}{\lambda_P} \neq 1$	$H_2: \frac{\lambda_L}{\lambda_P} = 1 \text{ vs } H_{21}: \frac{\lambda_L}{\lambda_P} \neq 1$	
Family 2: Time to First PE (Hazard Ratio)		
$H_3: \frac{h_H}{h_P} = 1 \text{ vs } H_{31}: \frac{h_H}{h_P} \neq 1$	$H_4: \frac{h_L}{h_P} = 1 \text{ vs } H_{41}: \frac{h_L}{h_P} \neq 1$	
Family 3: Responder Status for Exacerbation Free (Odds Ratio)		
$H_5$ : $\frac{\theta_H}{\theta_P} = 1$ vs $H_{51}$ : $\frac{\theta_H}{\theta_P} \neq 1$	$H_6: \frac{\theta_L}{\theta_P} = 1 \text{ vs } H_{61}: \frac{\theta_L}{\theta_P} \neq 1$	
Family 4: Change in Post-Bronchodilator FEV 1 at Week 52 (Mean Difference)		
$H_7: \mu^{(F)}_H - \mu^{(F)}_P = 0$	$H_8: \mu^{(F)}_L - \mu^{(F)}_P = 0$	
vs $H_{71}$ : $\mu^{(F)}_{H} - \mu^{(F)}_{P} \neq 0$	vs $H_{81}$ : $\mu^{(F)}_{L} - \mu^{(F)}_{P} \neq 0$	
Family 5: Annualized Rate of Severe PEs (Rate Ratio)		
$H_9$ : $\frac{\lambda_H}{\lambda_P} = 1$ vs $H_{91}$ : $\frac{\lambda_H}{\lambda_P} \neq 1$	$H_{10}$ : $\frac{\lambda_L}{\lambda_P} = 1$ vs $H_{101}$ : $\frac{\lambda_L}{\lambda_P} \neq 1$	
Family 6: Change in QoL-B Respiratory Symptoms Domain Score at Week 52 (Mean Difference)		
$H_{11}$ : $\mu^{(Q)}_{H} - \mu^{(Q)}_{P} = 0$	$H_{12}: \mu^{(Q)}_{L} - \mu^{(Q)}_{P} = 0$	
$vs H_{111}: \mu^{(Q)}_{H} - \mu^{(Q)}_{P} \neq 0$	$vs  H_{121} : \mu^{(Q)}_{L} - \mu^{(Q)}_{P} \neq 0$	

CONFIDENTIAL Page 29 of 139

Note: The subscript H to parameters  $(\lambda, \theta, \mu^{(F)}, \mu^{(Q)})$  denotes High Dose (Brensocatib 25 mg), the subscript L denotes Low Dose (Brensocatib 10 mg), and a subscript P denotes Placebo.

## **6.3.2.** Mixture-based gatekeeping procedure

The proposed mixture-based gatekeeping procedure includes the following features (Dmitrienko and Tamhane, 2011 and 2013, and Kordzakhia et al., 2018):

- A truncated version of the Hochberg test will be used in Family 1. The gatekeeping procedure will proceed to the next family even if only one comparison is significant (a single hypothesis is rejected) in Family 1.
- The Bonferroni test will be used in Families 2-5. The gatekeeping procedure will proceed to the next family even if only one comparison is significant (a single hypothesis is rejected) in the current family.
- The Hochberg test will be used in Family 6.

The test statistics within Families 1 and 6 follow a bivariate normal distribution with a positive correlation induced by the common placebo arm. Under these conditions, the positive dependence condition (MTP2 condition), which guarantees local Type I error rate control within these families, is met (Sarkar and Chang, 1997; Sarkar, 1998).

The closed testing representation is constructed based on pre-specified truncation parameters  $\gamma_k$ , for Family k (= 1,2,3,4,5,6). The above proposed procedure uses a testing algorithm based on  $\gamma_1$  = 0.9 for Family 1,  $\gamma_k$  = 0 for Family k(= 2,3,4,5), and  $\gamma_6$  = 1 for Family 6. This representation will be used to compute multiplicity-adjusted p-values for the 12 individual null hypotheses,  $H_1$ ,  $H_2$ ,  $H_3$ ,  $H_4$ ,  $H_5$ ,  $H_6$ ,  $H_7$ ,  $H_8$ ,  $H_9$ ,  $H_{10}$ ,  $H_{11}$ ,  $H_{12}$ .

The testing algorithm utilizes the closure principle and specifies the decision rule for each intersection hypothesis in the closed family associated with the 12 null hypotheses. The closed family contains  $2^{12} - 1 = 4095$  intersections of the original null hypotheses. Define an arbitrary index set as  $I \subseteq \{1,2,3,4,5,6,7,8,9,10,11,12\}$ . Let H(I) denote an arbitrary intersection hypothesis from the closed family, which is associated with the index set I. A local p-value, also known as the intersection p-value, will be computed for the intersection hypothesis H(I) as shown below using the raw p-values for the individual null hypotheses. The raw p-values are denoted by  $p_1$  through  $p_{12}$ .

To ensure that the procedure is consistent with the logical restrictions among the null hypotheses, the corresponding restrictions need to be imposed on the hypotheses within each intersection. These restrictions ensure, for example, that the null hypothesis  $H_3$  cannot be rejected if the null hypothesis  $H_1$  is not rejected ( $H_3$  will be automatically accepted if  $H_1$  is not rejected). Let  $I^*$  denote the restricted index set which accounts for the logical relationships among the null hypotheses within the intersection hypothesis H(I). For example, if the intersection hypothesis is given by  $H_1 \cap H_2 \cap H_3$ , the original index set is  $I = \{1, 2, 3\}$ . After the logical restrictions are imposed, the restricted index set is  $I^* = \{1, 2\}$  since the hypothesis  $H_3$  cannot be rejected if the null hypothesis  $H_1$  is not rejected.

CONFIDENTIAL Page 30 of 139

It is easy to show that, for any intersection hypothesis H(I), there can be at most two indices left in the restricted index set  $I^*$ . Because of this, it is sufficient to consider the following two cases:

Case 1. Suppose that there are two indices in the restricted index set  $I^*$  that are denoted by i and j, i.e.,  $I^* = \{i, j\}$ .

- a. If the corresponding hypotheses are included in the same family, the following subcases will be considered:
  - The Hochberg test is used in Families 1 and 6. Thus, the local p-value for this intersection hypothesis is constructed using the Simes approach, i.e., the local p-value is given by  $p(I) = \min(2\min(p_i, p_j), \max(p_i, p_j))$ , where  $I^* = \{1, 2\}$  for Family 1 and  $I^* = \{11, 12\}$  for Family 6.
  - Since the Bonferroni test is used in Families 2,3, 4, and 5, the local p-value for this intersection hypothesis is constructed using the Bonferroni approach, i.e., the local p-value is given by  $p(I) = 2\min(p_i, p_i)$ .
- b. If the corresponding hypotheses are included in two different families, let *i* denote the index corresponding to the more important family, the following subcases will be considered:
  - If the index i is equal to 1, the local p-value for this intersection hypothesis is given by  $p(I) = 2 \min(p_i/(1+\gamma_i), p_i/(1-\gamma_i))$ .
  - If the index i is greater than 1, the local p-value for this intersection hypothesis is given by  $p(I) = 2 \min(p_i, p_j)$ .

Case 2. Suppose that there is only one index in the restricted index set  $I^*$ , denoted by i, i.e.,  $I^* = \{i\}$ . In this case, the local p-value for the intersection hypothesis is simply given by  $p(I) = p_i$ .

The resulting local p-values for the intersection hypotheses in the closed family will be utilized for computing the multiplicity-adjusted p-values for the 12 null hypotheses. Specifically, consider the multiplicity-adjusted p-value for the null hypothesis  $H_i$ , i = 1, ... 12, which is denoted by  $\tilde{p}_i$ . This adjusted p-value is defined as the maximum over the local p-values for all intersection hypotheses that include  $H_i$ , i.e.,

$$\tilde{p}_i = \max_{i \in I} p(I)$$
.

A null hypothesis will be rejected if its adjusted p-value is less than or equal to a pre-defined significance level. The formulae of adjusted p-values of individual null hypotheses are provided in Appendix J.

In case Brensocatib is worse than Placebo in terms of point estimator in one or more of the 12 hypotheses, all 12 two-sided p-values will be converted to one-sided p-values when applying the mixture-based gatekeeping procedure, and the adjusted one-sided p-values will be converted back to adjusted two-sided p-values.

CONFIDENTIAL Page 31 of 139

#### 6.4. General Definitions and Derivations

#### 6.4.1. Definition of IP Completion and Study Completion

A participant will be considered as completing the IP if the question "Did the subject complete the planned treatment per protocol?" on the EOT form is answered with "Yes".

A participant will be considered as completing the study if the question "Did the subject complete the study?" on the EOS form is answered with "Yes".

# 6.4.2. Date of First / Last IP intake, Treatment Display in Data Tabulations, and Actual Treatment

Administration of IP is collected daily using an electronic diary. Participants are not able to enter missed doses retrospectively, while the very first dose may not be recorded. Participant's date of attending Visit 2 is used as the First Dose Date (SCH\_VS dataset [Visit Dataset]) as participants will receive their initial dose at the site. A date of first dose will be assigned only if records for IP administration were reported fulfilling the condition "Did you take your study medication today?" = "Yes" (for at least one record) in the drug administration form ("Dose Administration" within the Patient Cloud folder of the CRF). Participants attending Visit 2 but without any records in "Dose Administration" fulfilling the condition will be considered as not being treated with randomized IP.

The "Last dose date" entered in the EOT form will be used to determine the date of last administration of randomized IP.

If not stated otherwise, tabulations will be presented by treatment groups and overall using the following labelling throughout all displays:

- Brensocatib 10 mg;
- Brensocatib 25 mg;
- Placebo;
- All Participants (applicable study population summaries only, unless stated otherwise [see Section 6.9]),
- Pooled Brensocatib (applicable for all safety tables, unless stated otherwise).

The participant's actual treatment for the Safety, Pharmacodynamic, PK Concentration, and CT Scan Analysis Sets will be derived from exposure data. The Kit ID dispensed by the IRT and actual kit ID used will be recorded. If a participant's actual treatment is the same as the assigned treatment, then actual treatment is the assigned treatment. If a participant receives a study treatment that is different from the assigned treatment, then the following rule will apply:

• the actual treatment group will be set to placebo, brensocatib 10 mg or brensocatib 25 mg depending on the most common administered dose, regardless of the randomized treatment.

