### **5.3.** Study Treatment Administration

Brensocatib 10 mg, brensocatib 25 mg, or placebo will be administered QD by mouth with water in the morning before breakfast; tablets must not be broken or chewed. Subjects will be instructed to record each daily dose of study drug administered in an electronic dosing diary. On the days of clinical study visits, including Visit 11 (Week 52), study drug will be administered at the study site by study personnel after collection of all applicable patient-reported outcome measures (Section 7.5) and after sputum collection (Table 5).

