## 5.3. Safety Analysis Set

The Safety Analysis Set comprises all participants who were randomized and received at least 1 dose of brensocatib or placebo and will exclude participants from Ukraine and participants from site USA065. The Safety Analysis Set will be analyzed using the actual treatment received. Derivation of participants' actual treatment is detailed in Section 6.4.2.

Randomized participants who received at least 1 dose of IP will be included.

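### SAP 6.4.2 decides treated status from the e-diary alone, so a participant given the Visit 2 site dose but with no diary 'Yes' is classed as not treated

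*SAP*

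**What the plan says.** SAP 6.4.2 makes five statements about dosing data.

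- Source: "Administration of IP is collected daily using an electronic diary".
- No back-entry: "Participants are not able to enter missed doses retrospectively".
- Known gap: the sentence continues, "while the very first dose may not be recorded".
- First-dose date: the Visit 2 date is used, "as participants will receive their initial dose at the site".
- Gate: "A date of first dose will be assigned only if records for IP administration were reported fulfilling the condition", namely at least one 'Yes' to the daily question on whether study medication was taken. A Visit 2 attendee with no record "fulfilling the condition will be considered as not being treated with randomized IP".

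The Safety Analysis Set has no diary condition. SAP 5.3 says "Randomized participants who received at least 1 dose of IP will be included", and protocol 10.2.3 likewise requires only randomization and one dose. Protocol 5.3 says that on clinic visit days "study drug will be administered at the study site by study personnel". SAP Section 13, which lists departures from the protocol, does not mention the diary gate.

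**The concern.** The SAP names a gap in its data source and then lets that source alone decide who was treated. The participant caught by this has a dose that staff gave at the site, no diary entry for it, and no 'Yes' on any later day. One way to reach that state is to stop after the first dose. Intolerance is one possible reason for stopping then, so the omitted participants may not be typical.

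Without a first-dose date, several derivations fail:

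- The treatment-emergent window in SAP 9.2 has no start.
- Exposure duration (SAP 6.4.7) and time at risk for the On-IP and On-Treatment estimands (SAP Table 5) cannot be computed.
- SAP Section 2 removes randomized-but-untreated participants from the On-Treatment analysis.
- The disposition table (SAP 7.1) counts the person as not having received IP.

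**Working it through.** The plan states no figure that depends on this rule, so there is nothing to reproduce. The check is logical.

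**Step 1. Enumerate the cases.** True status is treated if the site dose was given or a later dose was taken. Status under SAP 6.4.2 is treated if the diary has any 'Yes', whether for the site dose or later. A later 'Yes' is taken to be truthful.

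| Site dose given | Site dose in diary | Any later 'Yes' | True status | SAP 6.4.2 |
|---|---|---|---|---|
| yes | yes | yes | treated | treated |
| yes | yes | no | treated | treated |
| yes | no | yes | treated | treated |
| yes | no | no | treated | **not treated** |
| no | no | yes | treated | treated |
| no | no | no | not treated | not treated |

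One of the six cases is wrong. A single 'Yes' at any time in the study is enough for correct classification. The fourth row also covers someone who kept taking tablets but never made a diary entry.

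**Step 2. Look for another rule.** SAP 5.3 refers to 6.4.2 only for actual treatment received, not for whether any dose was received. No other section says how receipt of a dose is established. Exclusion from the Safety Analysis Set is therefore an inference, drawn from 6.4.2 being the only operational rule available.

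**Step 3. Set this against other dosing data in the plan.**

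- The EOT form's 'Last dose date' defines last intake (SAP 6.4.2) and the onset of early IP discontinuation as an intercurrent event (SAP 6.2.1.1). A participant could have a last dose and an IP discontinuation, but no first dose.
- Protocol 8.2 and Appendix 5 schedule Day 1 postdose PK samples: 0.5 hour, 2 hours and 4 to 8 hours in the substudy, and an optional 2-hour sample in other adults. A participant with measurable drug on Day 1 could be classed as untreated.
- Dispensed and returned tablet counts are used for compliance (SAP 6.4.7). If the returned count is missing, that section assumes nothing was taken from the kit.

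**Step 4. Illustrate the size (assumed numbers only).** Take the planned 540 adults per arm and assume that 27 have some adverse event: 27/540 = 5.0%. Remove k misclassified participants from the arm.

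- If all k had the event, incidence = (27 − k)/(540 − k). For k = 1, 3, 5, 10 this gives 4.82%, 4.47%, 4.11%, 3.21%.
- If none had it, incidence = 27/(540 − k). The same k give 5.01%, 5.03%, 5.05%, 5.09%.

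The shift can go either way. It depends on k and on who the omitted people are, and the documents give neither.

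**The case against.** The strongest reply is that this is a corner case that existing steps would expose.

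- SAP 6.2 plans a blinded data review of analysis-set assignment, documented and signed before lock.
- Protocol 10.4.1 lists participants excluded from any set, with reasons.
- SAP 7.1 tabulates those who did not receive IP, and SAP 9.1 counts randomized-but-untreated participants separately.
- SAP 9.2 lists non-treatment-emergent events, and protocol 10.4.7.1 lists all AEs.
- The dosing diary is brought to every in-clinic visit (protocol 5.5), so 52 weeks without one 'Yes' is improbable in someone who keeps taking drug.

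Much of this stands: the long-term non-recorder is remote, and affected participants should be visible. Two things remain. The review meeting is given no alternative dosing source and no authority to override 6.4.2, so applying the SAP as written would confirm the exclusion. The first in-clinic visit after Visit 2 is at Week 4, so diary review does not help with someone who stops after the first dose.

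A reader might infer more than the documents support:

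- **That safety tables are biased in favour of brensocatib.** The rule applies equally to placebo, and step 4 shows that the direction depends on unknown facts.
- **That early stoppers are removed as such.** An early stopper with one 'Yes' is kept. The SAP says that the first dose may go unrecorded, not that it always does.
- **That a percentage of the trial is lost.** No share without a 'Yes' is given, and that group would also contain people who truly took nothing.

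**Conclusion.** The rule as written gives a wrong answer for one identifiable type of participant: dosed at the site at Visit 2, with no diary 'Yes' at any time. That conflicts with the one-dose definition in SAP 5.3 and protocol 10.2.3. Loss from the Safety Analysis Set is an inference, though a strong one, because no other rule for treated status exists.

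The number affected is not stated and may be small or zero. ITT membership and the primary On-Study analysis do not depend on the rule. The effect on the supplementary efficacy estimands is negligible for a Day 1-only participant, who would contribute one day at risk (last − first + 1 = 1). No between-arm bias is shown. This is a cheap correction to the safety derivations, best made before unblinding, because restoring participants afterwards would look post hoc.

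**What to change.** In SAP 6.4.2, keep the Visit 2 date as the first-dose date and class a participant as treated if any of these is present:

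- a diary 'Yes';
- a non-missing EOT 'Last dose date';
- a quantifiable post-dose brensocatib concentration, confirmed without unblinding the study team;
- source documentation that the dose was given at the site at Visit 2.

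Use tablet accountability only as support, and only when the returned count is recorded: unreturned tablets are not proof of intake. Class a participant as not treated only when all sources are negative. List discordant cases, then resolve and document them at the planned blinded data review meeting before database lock.

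Two cautions apply. A plasma concentration can confirm dosing only in the active arms, so the other sources must be checked equally for everyone. The documents also do not show an eCRF field for site administration at Visit 2, so that item may need a site query.

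The cost is SAP wording, one derivation that draws mainly on data already collected, and queries limited to participants with no 'Yes'. Trial conduct does not change.
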